5 STUDY ACTIVITIES

5.1 Eligibility Criteria

Subjects must meet all of the following criteria to be included in the study. Anything other than a positive response to the questions below will result in exclusion from study participation.

Consent

- ✔ 1. Subjects must voluntarily **sign and date an informed consent**, approved by an Independent Ethics Committee (IEC)/Institutional Review Board (IRB), before the initiation of any screening or study-specific procedures.
- ✔ 2. All subjects enrolled in this trial must be registered and must comply with all requirements of the pomalidomide risk evaluation and mitigation strategies (REMS) program or local equivalent.

Demographic and Laboratory Assessments

- ✔ 3. Adult **male or female**, at least 18 years old.
- ✔ 4. **Laboratory values** meeting the following criteria within the screening period before the first dose of study drug:
 - serum alanine aminotransferase (ALT) $\leq 3 \times$ the upper limit of normal (ULN)
 - aspartate aminotransferase (AST) $\leq 3 \times$ ULN
 - total bilirubin $\leq 1.5 \times$ ULN (subject with documented Gilbert's syndrome may be allowed total bilirubin $> 1.5 \times$ ULN)
 - creatinine clearance (CrCL) ≥ 30 mL/min, measured by 24-hour urine collection or calculated using the Cockcroft-Gault formula
 - prothrombin/international normalized ratio (INR) and/or activated partial thromboplastin time (aPTT) $\leq 1.5 \times$ normal limits
 - ANC $> 1,000/\mu\text{L}$ (growth factor support is allowed to achieve eligibility criteria)
 - platelet count
 - $\geq 75,000/\text{mm}^3$ for subjects with $\leq 50\%$ myeloma involvement in the bone marrow
 - $\geq 50,000/\text{mm}^3$ for subjects with $> 50\%$ myeloma involvement in the bone marrow
 - no platelet transfusion ≤ 72 hours before screening platelet count
 - hemoglobin ≥ 8.0 g/dL (subject must not receive a blood transfusion within 72 hours before screening hemoglobin)
- ✔ 5. Are willing or able to comply with procedures required in this protocol.

Disease Activity

- ✓ 6. R/R MM with documented evidence of progression during or after the subject's last treatment regimen based on the investigator's determination of the International Myeloma Working Group (IMWG) criteria.
- ✓ 7. Measurable disease, defined by at least 1 of the following disease activity criteria:
 - serum M-protein ≥ 1.0 g/dL (≥ 10 g/L) for IgG MM
 - serum M-protein ≥ 0.5 g/dL (≥ 5 g/L) for IgA, IgD, IgE, and IgM MM
 - urine M-protein ≥ 200 mg/24 hours

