- Collect only for subjects without measurable M-protein in screening serum or urine.
- Urine protein electrophoresis and urine immunofixation collection is mandatory for confirmation of VGPR, CR, and sCR, regardless of whether urine M-protein was measurable at baseline.
- An MRD assessment will be required for every response of \geq VGPR AND if subject is to be discontinued for progressive disease AND 6 and 12 months post-confirmation of CR/sCR for subjects who have maintained this response.

- j. Pomalidomide education and counseling guidance document for each gender as well as pomalidomide information sheet must be completed and signed before starting pomalidomide and each time the subject receives a new supply of pomalidomide.

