Analysis of serum protein immunofixation, serum protein electrophoresis, serum quantitative immunoglobulins, serum free-light chains (FLCs), urine protein immunofixation, urine protein electrophoresis, plasmacytoma evaluation (if applicable), skeletal survey, and bone marrow aspirate and biopsy will be utilized for disease assessment. Subjects will be evaluated using the International Myeloma Working Group (IMWG) 2016 criteria for disease response and progression.¹⁵ All local laboratory results must be entered into the eCRF.

Laboratory Tests for Multiple Myeloma

All serum and urine laboratory tests for IMWG assessments must be sent to a certified central laboratory and may also be collected and sent to the local laboratory per the investigator's discretion. IMWG assessments per protocol should not be made using local laboratory values (except for bone marrow and imaging).

Serum protein immunofixation, serum protein electrophoresis, serum quantitative immunoglobulins, serum FLCs, urine protein immunofixation, and urine protein electrophoresis may be performed approximately 7 days before the scheduled visit day.

Serum Protein Electrophoresis, Serum Protein Immunofixation, Serum Quantitative Immunoglobulins

Blood samples for serum protein electrophoresis, serum protein immunofixation, and serum quantitative immunoglobulin testing will be collected as outlined in [Table 4](#). Serum protein electrophoresis and serum immunofixation will be collected for all subjects at baseline and throughout the study until progressive disease (PD) or withdrawal of consent, regardless of serum protein electrophoresis being measurable or monoclonal-protein (M-protein) presence at baseline.

Importantly, the assessment of serum protein electrophoresis M-protein and serum immunofixation at the time of possible VGPR or complete response (CR)/stringent complete response (sCR) is mandatory, even in subjects without measurable values at baseline.

Serum Free Light Chains

Blood samples for serum FLC testing will be collected for all subjects as outlined in [Table 4](#).

Subjects with measurable disease in either serum protein electrophoresis and/or urine protein electrophoresis will be assessed for response only based on these 2 tests and not by the FLC assay. FLC response criteria are only applicable to subjects without measurable disease in the serum or urine protein electrophoresis and to fulfill the requirements of sCR or CR per IMWG criteria.¹⁵

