Measurable disease are lesions that can be accurately measured in 2 dimensions and both diameters must be ≥ 20 mm when evaluated by standard CT scanning or ≥ 10 mm when evaluated by spiral CT scanning. Nonmeasurable disease are all other lesions (or sites of disease), including those that are too small (i.e., do not meet above criteria), occur within a previously irradiated area (unless they are documented as new lesions since the completion of radiation therapy), bone lesions, leptomeningeal disease, ascites, pleural or pericardial effusion (exception for effusions documented by cytology as not malignant or present at baseline without progression), lymphangitis cutis/pulmonis, abdominal masses that are not pathologically/cytologically confirmed and followed by imaging techniques, and cystic lesions.

Bone Marrow Aspirate and Biopsy

Bone marrow aspirate and biopsy should be completed as outlined in [Table 4](#). Bone marrow aspirates and biopsies performed as standard of care throughout the study should also be captured on an eCRF.

A sufficient bone marrow aspirate or biopsy must be collected for clinical assessment (pathology) performed by central laboratory as well as for shipment of a portion to AbbVie (or designee) for the biomarker analyses. Samples should be assessed for IWMG first, then split for biomarker analysis.

Assessment of bone marrow for percentage plasma cells is required within 21 days before the first dose for baseline assessment (screening visit) and while on study to confirm CR (i.e., subjects who become immunofixation negative) or at time of suspected disease progression, if clinically indicated.

Bone marrow plasma cell clonality must also be evaluated at the time of CR (< 5% plasma cells) to assess for sCR, if applicable. Flow cytometry is preferred over immunohistochemistry (IHC) for assessment of clonality by κ and λ staining. Flow cytometry will be performed only to assess for sCR locally per institution standard practice. If local flow cytometry to assess clonality is not available at the time of CR, a core biopsy and/or clot section should be evaluated by IHC staining for κ or λ or light chain restriction. To confirm a CR, a second confirmation bone marrow analysis for CR is not needed.

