APPENDIX F. IMWG RESPONSE CRITERIA FOR MULTIPLE MYELOMA (2016)

Response Subcategory	Response Criteria ^a
Stringent complete response*	
 Negative immunofixation on the serum and urine (regardless of whether disease at baseline was measurable in serum, urine, both, or neither) and Disappearance of any soft tissue plasmacytomas and < 5% plasma cells in bone marrow^b and Normal FLC ratio** and Absence of clonal cells in bone marrow^b by immunohistochemistry (κ/λ ratio $\leq 4:1$ or $\geq 1:2$ for κ and λ patients, respectively, after counting ≥ 100 plasma cells)^c
Complete response* ^c	
 Negative immunofixation on the serum and urine (regardless of whether disease at baseline was measurable on serum, urine, both, or neither) and Disappearance of any soft tissue plasmacytomas and < 5% plasma cells in bone marrow^b and For subjects in whom the only measurable disease is by serum FLC levels, a normal FLC ratio** is also required
Very good partial response*	
 Serum and urine M-protein detectable by immunofixation but not on electrophoresis or $\geq 90\%$ reduction in serum M-protein plus urine M-protein < 100 mg per 24 hours For subjects in whom the only measurable disease is by serum FLC levels, VGPR is defined as: 
 $\geq 90\%$ decrease in the difference between involved and uninvolved FLC levels
Partial response	
 $\geq 50\%$ reduction of serum M-protein and Reduction in 24-hour urinary M-protein by $\geq 90\%$ or to < 200 mg per 24 hours 
 If the serum and urine M-protein are unmeasurable,^d a $\geq 50\%$ decrease in the difference between involved and uninvolved FLC levels is required in place of the M-protein criteria If the serum and urine M-protein are unmeasurable,^d and serum-free light assay is also unmeasurable, a $\geq 50\%$ reduction in plasma cells is required in place of M-protein provided baseline bone marrow plasma-cell percentage was $\geq 30\%$ $\geq 50\%$ reduction in the size of soft tissue plasmacytomas is also required, if present at baseline
Minimal response	
 25% – 49% reduction of serum M-protein and 50% – 89% reduction in 24-hour urinary M-protein and $\geq 50\%$ reduction in the size (SPD)^f of soft tissue plasmacytomas if present at baseline

Response Subcategory	Response Criteria ^a

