CR = complete response; CRAB = calcium elevation, renal failure, anemia, lytic bone lesions; CT = computed tomography; FLC = free-light chain; IMWG = International Myeloma Working Group; M-protein = monoclonal-protein; MR = minimal response; MRI = magnetic resonance imaging; PET = positron emission tomography; PR = partial response; SPD = sum of the products of the maximal perpendicular diameters of measured lesions; VGPR = very good partial response

- a. All response categories require 2 consecutive assessments made at any time before the institution of any new therapy; all categories also require no known evidence of progressive or new bone lesions or extramedullary plasmacytomas if radiographic studies were performed. Radiographic studies are not required to satisfy these response requirements.
- b. Confirmation with repeat bone marrow biopsy not needed.
- c. Presence/absence of clonal cells on immunohistochemistry is based upon the k/λ ratio. An abnormal k/λ ratio by immunohistochemistry requires a minimum of 100 plasma cells for analysis. An abnormal ratio reflecting presence of an abnormal clone is k/λ of > 4:1 or < 1:2.
- d. Measurable disease is defined as meeting at least one of the following 3 measurements: serum M-protein ≥ 1 g/dL (≥ 10 g/L) or urine M-protein ≥ 200 mg/24 hours or serum FLC assay with an involved FLC level ≥ 10 mg/dL (≥ 100 mg/L) provided serum FLC ration is abnormal.
- e. Not recommended for use as an indicator of response; stability of disease is best described by providing the time to progression estimates.
- f. Plasmacytoma measurements should be taken from the CT portion of the PET/CT, or MRI scans, or dedicated CT scans where applicable. For patients with only skin involvement, skin lesions should be measured with a ruler. Measurement of tumor size will be determined by the SPD.

Notes:

- * Clarification to IMWG criteria for coding CR and VGPR in subjects whom the only measurable disease is by serum FLC levels. In these subjects, CR is defined as a normal FLC ratio of 0.26 to 1.65 in addition to CR criteria listed above, and VGPR is defined as a ≥ 90% decrease in the difference between involved and uninvolved FLC levels.
- ** Serum and urine M-protein testing is required to fulfill requirements of VGPR and CR categories regardless of whether disease at baseline was measurable in serum, urine, both, or neither.

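### Criterion 7 admits non-IgG subjects at a serum M-protein of 0.5 g/dL, but the partial-response rule calls anything under 1 g/dL unmeasurable, so some eligible subjects have no workable PR route

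*Protocol*

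**What the plan says.** **Eligibility.** Protocol 5.1, criterion 7, defines measurable disease. For IgG the serum limit is 1.0 g/dL; for the other isotypes it is lower: "serum M-protein ≥ 0.5 g/dL (≥ 5 g/L) for IgA, IgD, IgE, and IgM MM". The synopsis repeats both limits.

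**Response.** Appendix F footnote d defines the same term without an isotype split: "Measurable disease is defined as meeting at least one of the following 3 measurements: serum M-protein ≥ 1 g/dL (≥ 10 g/L". Its urine limb (200 mg/24 h) and FLC limb (10 mg/dL with an abnormal ratio) match criterion 7; only the serum limb differs. Footnote d is attached to the word *unmeasurable* in the PR row, where it switches the rule:

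- Serum and urine unmeasurable: a fall of at least 50% applies to FLC, so that a "decrease in the difference between involved and uninvolved FLC levels is required in place of the M-protein criteria".
- FLC unmeasurable as well: a 50% "reduction in plasma cells is required in place of M-protein provided baseline bone marrow plasma-cell percentage was" at least 30%.

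**Scoring and collection.** Appendix E (Serum Free Light Chains) says that subjects with measurable disease on serum or urine electrophoresis "will be assessed for response only based on these 2 tests and not by the FLC assay". The same section says "Blood samples for serum FLC testing will be collected for all subjects as outlined in" Table 4. Footnote b of that table and footnote g of Appendix D both restrict the on-treatment samples: "Collect only for subjects without measurable M-protein in screening serum or urine". None of these places gives a threshold or points to one.

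**Marrow.** Appendix E requires plasma-cell percentage at screening and "while on study to confirm CR (i.e., subjects who become immunofixation negative) or at time of suspected disease progression, if clinically indicated". Table 4 schedules marrow at confirmation of CR or sCR, with an optional sample at end of treatment. Appendix D footnote i adds MRD sampling at VGPR or better.

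**The concern.** A subject can be enrolled because the serum M-protein is measurable, and then be scored under a rule that treats it as unmeasurable. The M-protein rule and the FLC or marrow rule exclude each other for PR, so the choice of definition can decide whether a subject counts as a responder.

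ORR, meaning PR or better, is the primary efficacy endpoint. Each investigator scores it (Appendix E, Evaluation of Disease), and SAP 4.3.1 lists the qualifying categories without a measurability rule. The expansion arms are small (about 23 and 27) and, under SAP 4.5, are monitored continuously and open-label. A definition settled only after responses are known would be hard to defend.

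**Working it through.** **1. Who is affected.** Only eligible non-IgG subjects with serum M-protein from 0.5 to below 1.0 g/dL and urine M-protein below 200 mg/24 h. The two definitions agree for IgG disease, for serum at or above 1 g/dL, and for urine at or above 200 mg/24 h.

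**2. Case (1): FLC also unmeasurable.**

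| Baseline marrow plasma cells | PR route under criterion 7 | PR route under footnote d |
|---|---|---|
| below 30% | serum M-protein fall | none |
| 30% or more | serum M-protein fall | marrow fall, but no on-treatment marrow is scheduled to document PR |

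VGPR and CR stay open. The M-protein route to VGPR is replaced only where FLC is the sole measurable disease, and CR applies whatever was measurable at baseline. Appendix E makes electrophoresis and immunofixation mandatory at possible VGPR or CR even without measurable baseline values. What drops out of ORR is a best response of exactly PR.

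**3. Case (2): FLC measurable.** Either definition gives usable data if it is applied throughout. Serial FLC is missing only if a site uses criterion 7 to decide collection and footnote d to decide scoring. Even with complete data the two can disagree (assumed values):

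- IgA, serum 0.7 to 0.3 g/dL: (0.7 − 0.3)/0.7 = 57% fall. FLC difference 20 to 12 mg/dL: (20 − 12)/20 = 40% fall. PR under criterion 7 only.
- IgA, serum 0.8 to 0.6 g/dL: (0.8 − 0.6)/0.8 = 25% fall, with a fall of at least 50% in the FLC difference. PR under footnote d only.

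**4. Size.** Inputs (Protocol 7.2 and 7.4; SAP 4.4 and 6.1): null ORR 0.35. Arm A: n = 23, target p = 0.70, one-sided 0.025. Arm B: n = 27, target p = 0.60, one-sided 0.1.

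The cut-off is the smallest r with P(X ≥ r | n, 0.35) at or below the significance level.

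- Arm A: P(X ≥ 14) = 0.0100 and P(X ≥ 13) = 0.0283, so r = 14.
- Arm B: P(X ≥ 14) = 0.0536 and P(X ≥ 13) = 0.1106, so r = 14.

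The plan states 90% power in each arm. Exact power is P(X ≥ 14 | 23, 0.70) = 0.8799 and P(X ≥ 14 | 27, 0.60) = 0.8553. That shortfall is a separate matter; these exact values are the baseline here.

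One subject is 1/23 = 4.3 points of ORR in Arm A and 1/27 = 3.7 points in Arm B. One subject decides the test only when the count sits at the cut-off.

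Now assume one case (1) subject per arm, scored under footnote d, and let v be the share of responders who reach VGPR or better. That subject counts with probability p·v instead of p, and matters only if the other n − 1 subjects give exactly 13 responses:

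new power = exact power − p(1 − v) · P(Y = 13), with Y ~ Binomial(n − 1, p).

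P(Y = 13) is 0.0949 for Binomial(22, 0.70) and 0.0911 for Binomial(26, 0.60).

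| Arm | v = 0.25 | v = 0.75 |
|---|---|---|
| A | 0.8799 − 0.70 × 0.75 × 0.0949 = 0.830 | 0.8799 − 0.70 × 0.25 × 0.0949 = 0.863 |
| B | 0.8553 − 0.60 × 0.75 × 0.0911 = 0.814 | 0.8553 − 0.60 × 0.25 × 0.0911 = 0.842 |

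**The case against.** The strongest reply is that the protocol does supply a hierarchy. Appendix E sends response assessment to Appendix F, both under IMWG Criteria for Response and Progression and under Evaluation of Disease. Footnote d sits on the PR row itself, while criterion 7 sits in the eligibility list and does not claim to score response. A reader might infer that nothing says which definition governs. The documents do not support that: for PR, footnote d is the more natural reading.

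This stands, but it does not remove the problem. Following footnote d is what produces the case (1) gap. The Appendix E rule on electrophoresis versus FLC and the two FLC collection footnotes still use *measurable* without a threshold or a cross-reference, so a site may apply criterion 7 there.

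It is also fair that no passage tells a site to mix definitions, that the affected group may be very small, that the primary objective is safety, and that SAP 4.5 bases the final go/no-go on all efficacy and safety data together. These points limit the consequence without making the two definitions agree.

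**Conclusion.** The contradiction is real and narrow. For an eligible non-IgG subject in the band, with FLC unmeasurable, footnote d as written blocks a best response of exactly PR. With FLC measurable, the two definitions can classify the same data differently, in either direction.

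The number of affected subjects is unknown. With one case (1) subject per arm, the power loss is about 1.7 to 5.0 points in Arm A and 1.4 to 4.1 points in Arm B. Both the single subject and the 25% to 75% share reaching VGPR or better are assumptions, not figures from the documents. The Arm A figures use the protocol's 23; SAP 4.5 speaks of around 29 once escalation subjects are added.

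Three stronger readings are tempting and are not supported:

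- *Affected subjects can never be responders.* VGPR and CR still count towards ORR.
- *The type I error is inflated.* Neither definition makes anyone an automatic responder.
- *The conflict carries over to every response category.* The FLC-only CR and VGPR rules, the MR exclusion and the FLC and marrow PD rules also use *measurable* without a threshold, so they may be affected. Footnote d, however, is attached only to the PR row.

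**What to change.** Use one definition of measurable disease for eligibility, on-treatment FLC collection and response scoring. The simplest route is to give the serum limb of Appendix F footnote d the isotype limits of criterion 7 and leave its urine and FLC limbs unchanged. Every subject eligible on serum M-protein can then be scored from the electrophoresis already collected each cycle. Aligning the other places to the present footnote d is also possible, but it would leave the case (1) gap open.

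Cite the single definition in the Appendix E free-light-chain text, Table 4 footnote b, Appendix D footnote g and SAP 4.3.1. Date the decision, state whether response data had been seen, and apply it to all subjects, including those already treated.

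Report ORR under the present footnote d as a sensitivity analysis only for subjects who have the FLC or marrow data. State that routine on-treatment FLC will otherwise be missing in the affected subjects, because under this fix the collection footnotes no longer call for it.

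The cost is wording changes in five places and one sensitivity table, with no new samples or procedures. The drawback is that scoring departs from the present Appendix F text for a small subgroup. That should be noted when ORR is compared with the 35% historical rate.

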Potassium ≥ 0.5 mmol/L increase from prior value (even if potassium within normal limits [WNL])	
 Recheck potassium, phosphorus, uric acid, calcium, and creatinine in 1 hour immediately. If further ≥ 0.2 mmol/L increase in potassium, but still $<$ upper limit of normal (ULN), manage as per potassium \geq ULN. Otherwise recheck in 1 hour. Resume per protocol testing if change in potassium is < 0.2 mmol/L, potassium $<$ ULN, and no other evidence of tumor lysis. At discretion of investigator, may recheck prior to hospitalization. If stable or decreased and still WNL, hospitalization is at the discretion of the investigator. Potassium, phosphorus, uric acid, calcium, and creatinine must be rechecked within 24 hours.
Potassium $>$ ULN	
 Perform immediate ECG and commence telemetry. Nephrology (or acute dialysis service or other) notification with consideration of initiating dialysis. Administer kayexalate 60 g (or Resonium A 60 g). Administer furosemide 20 mg IV \times 1. Administer calcium gluconate 100 to 200 mg/kg IV slowly if there is ECG/telemetry evidence of life threatening arrhythmias. Recheck potassium, phosphorus, uric acid, calcium, and creatinine in 1 hour immediately. If potassium $<$ ULN 1 hour later, repeat potassium, phosphorus, uric acid, calcium, and creatinine 1, 2, and 4 hrs, if no other evidence of tumor lysis.

Abnormality	Management Recommendations
Hyperkalemia (Including Rapidly Rising Potassium) (continued)	

Potassium \geq 6.0 mmol/L (6.0 mEq/L) and/or symptomatic (e.g., muscle cramps, weakness, paresthesias, nausea, vomiting, diarrhea)
	
 • Perform immediate ECG and commence telemetry. • Nephrology (or acute dialysis service or other) assessment with consideration of initiating dialysis. • Administer kayexalate 60 g (or Resonium A 60 g). • Administer furosemide 20 mg IV \times 1. • Administer insulin 0.1 U/kg IV + D25 2 mL/kg IV. • Administer sodium bicarbonate 1 to 2 mEq/kg IV push. 
 • If sodium bicarbonate is used, rasburicase should not be used as this may exacerbate calcium phosphate precipitation. • Administer calcium gluconate 100 to 200 mg/kg IV slowly if there is ECG/telemetry evidence of life threatening arrhythmias. Do not administer in same IV line as sodium bicarbonate. • Recheck potassium, phosphorus, uric acid, calcium, and creatinine every hour immediately.
Hyperuricemia	

Uric acid \geq 8.0 mg/dL (476 μmol/L)
	
 • Consider rasburicase (dose per institutional guidelines). 
 • If rasburicase is used, sodium bicarbonate should not be used as this may exacerbate calcium phosphate precipitation. • Recheck potassium, phosphorus, uric acid, calcium, and creatinine in 1 hr immediately.

Uric acid \geq 10 mg/dL (595 μmol/L) OR Uric acid \geq 8.0 mg/dL (476 μmol/L) with 25% increase and creatinine increase \geq 0.3 mg/dL (\geq 0.027 mmol/L) from predose level
	
 • Administer rasburicase (dose per institutional guidelines). 
 • If rasburicase is used, sodium bicarbonate should not be used as this may exacerbate calcium phosphate precipitation. • Consult nephrology or acute dialysis service (or other). • Recheck potassium, phosphorus, uric acid, calcium, and creatinine in 1 hr immediately. 
 • If uric acid $<$ 8.0 mg/dL 1 hour later, repeat potassium, phosphorus, uric acid, calcium, and creatinine 2 and 4 hrs later, if no other evidence of tumor lysis.

Abnormality	Management Recommendations
Hypocalcemia	
Calcium \leq 7.0 mg/dL (1.75 mmol/L) AND Patient symptomatic (e.g., muscle cramps, hypotension, tetany, cardiac arrhythmias)	
 • Administer calcium gluconate 50 to 100 mg/kg IV slowly with ECG monitoring. • Telemetry. • Recheck potassium, phosphorus, uric acid, calcium, and creatinine in 1 hr immediately. • If calcium normalized 1 hr later, repeat potassium, phosphorus, uric acid, calcium, and creatinine 2 and 4 hrs later, if no other evidence of tumor lysis. • Calculate corrected calcium and check ionized calcium if albumin low.
Hyperphosphatemia	
Phosphorus \geq 5.0 mg/dL (1.615 mmol/L) with \geq 0.5 mg/dL (0.16 mmol/L) increase	
 • Administer a phosphate binder (e.g., aluminum hydroxide, calcium carbonate, sevelamer hydroxide, or lanthanum carbonate). • Nephrology (or acute dialysis service or other) notification (dialysis required for phosphorus \geq 10 mg/dL). • Recheck potassium, phosphorus, uric acid, calcium, and creatinine in 1 hr immediately. • If phosphorus $<$ 5.0 mg/dL 1 hour later, repeat potassium, phosphorus, uric acid, calcium, and creatinine 2 and 4 hrs later, if no other evidence of tumor lysis.
Creatinine	
Increase \geq 25% from baseline	
 • Start or increase rate of IV fluids. • Recheck potassium, phosphorus, uric acid, calcium, and creatinine in 1 to 2 hrs immediately.

ECG = electrocardiogram; IV = intravenous

APPENDIX I. RECOMMENDED DOSE REDUCTIONS RELATED TO DRUG TOXICITIES AND USE WITH CONCOMITANT MEDICATIONS

If a subject reports taking any over-the-counter or prescription medications, vitamins and/or herbal supplements or if administration of any medication becomes necessary from 30 days before the screening visit through 30 days after last dose of study drug, the name of the medication, dosage information including dose, route, and frequency, date(s) of administration including start and end dates, and reason for use must be recorded on the appropriate electronic Case Report Form (eCRF).

Subjects should receive full supportive care during study participation, including transfusion of blood products, fluid and electrolyte replacement, and antibiotics when appropriate. Subjects who use oral contraceptives, hormone-replacement therapy, or other maintenance therapy should continue their use. For guidance regarding medications for management of tumor lysis syndrome (TLS) and neutropenia, refer to Section 6.4.

General guidelines regarding prohibited, cautionary, and allowed medications are summarized in Section 5.3 and Section 5.4. A sample list of prohibited and cautionary medications that may interact with study drugs is provided in [Appendix J](#). It is not possible to produce a complete list of medications that fall into these categories; if in question, please refer to the appropriate product label.

Concomitant administration of moderate or strong cytochrome P450 (CYP)3A and strong CYP1A2 inhibitors is prohibited during Part 1 (dose escalation), Cycle 1. Use of strong or moderate CYP3A inhibitors and strong CYP1A2 inhibitors is allowed (with appropriate venetoclax and pomalidomide dose reductions, respectively) after Part 1 (dose escalation), Cycle 1 and throughout the study for subjects enrolled in Part 2 (dose expansion) if no appropriate therapeutic alternative exists. Venetoclax dose reductions for concomitant administration with moderate or strong CYP3A inhibitors are presented in [Table 7](#). Subjects should be monitored more closely for signs of toxicities and the venetoclax dose may need to be further reduced. Pomalidomide dose reductions for concomitant use with strong CYP1A2 inhibitors are presented in [Table 8](#). Subjects should be monitored more closely for signs of toxicities and the venetoclax dose may need to be further reduced. After discontinuation of the CYP3A inhibitor, wait for 3 days before venetoclax dose is increased back to the target dose.

Concomitant administration of moderate or strong CYP3A inducers is prohibited during Cycle 1 (dose escalation), Part 1. After completion of Cycle 1 (dose escalation), Part 1, and throughout the study for subjects enrolled in Part 2 (dose expansion), concomitant use of moderate or strong CYP3A inducers should still be avoided. Alternative treatments with less CYP3A induction should be considered.

Study drug dose levels are presented in [Table 9](#). Toxicities related to venetoclax, pomalidomide, and dexamethasone are presented in [Table 10](#), [Table 11](#), and [Table 12](#), respectively.

Table 7. Dose Modifications for Venetoclax with Concomitant Moderate and Strong CYP3A Inhibitor Use

Venetoclax Dose with No Moderate or Strong CYP3A Inhibitor	Venetoclax Dose if Co-Administered with a Moderate CYP3A Inhibitor	Venetoclax Dose if Co-Administered with a Strong CYP3A Inhibitor
400 mg	200 mg	100 mg
600 mg	300 mg	100 mg
800 mg	400 mg	200 mg

CYP = cytochrome P450

Table 8. Dose Modifications for Pomalidomide with Concomitant Strong CYP1A2 Inhibitor Use

Assigned Pomalidomide Dose	Pomalidomide Dose if Co-Administered with a Strong CYP1A2 Inhibitor
4 mg	2 mg

CYP = cytochrome P450

The AbbVie Therapeutic Area Medical Director (TA MD) identified in [Appendix L](#) should be contacted if there are any questions regarding concomitant or prior therapy(ies) and venetoclax or pomalidomide dose reductions.

Table 9. Study Drug Dose Levels

Dose	Venetoclax	Pomalidomide	Dexamethasone (< 75 years of age)	Dexamethasone (≥ 75 years of age)
Starting dose	800 mg	4 mg	40 mg	20 mg
Dose level –1	600 mg	3 mg	20 mg	12 mg
Dose level –2	400 mg	2 mg	12 mg	8 mg
Dose level –3	200 mg	1 mg	8 mg	4 mg

Table 10. Toxicities Related to Venetoclax

Toxicities	Recommended Action
Grade 3 or Grade 4 neutropenia with infection or fever; or Grade 4 hematologic toxicities (except for lymphopenia)	
 • G-CSF or growth factors for neutropenia should be administered with venetoclax if clinically indicated. • For Grade 4 neutropenia (ANC < 500 cells/μL) without infection, anti-infective prophylaxis (e.g., amoxicillin/clavulanic acid or levofloxacin or equivalent per institutional guidelines) is recommended until the neutropenia improves to Grade 3 or better (ANC > 500 cells/μL). • First episode: Interrupt venetoclax and once the toxicity has resolved to Grade 1 or baseline level, venetoclax may be resumed at the same dose. • For subsequent episodes: Interrupt venetoclax. Consider using G-CSF as clinically indicated. Follow dose reduction guidelines when resuming treatment with venetoclax after resolution. A larger dose reduction may occur at the discretion of the investigator and according to the dose reduction guidelines.
Grade \geq 3 or serious infections	
 • Interrupt venetoclax and upon resolution, treatment can either be resumed at a reduced dose (see Table 9) or discontinued, at the discretion of the investigator.
Grade 3 or 4 non-hematologic events	
 • First episode: Interrupt venetoclax. Once toxicity has resolved to Grade \leq 1 or baseline, venetoclax may be resumed at the same dose. No dose modification is required. • For subsequent episodes: Interrupt venetoclax. Follow dose reduction guidelines when resuming treatment with venetoclax after resolution. A larger dose reduction may occur at the discretion of the investigator and according to the dose reduction guidelines.
Blood chemistry changes or symptoms suggestive of TLS	
 • Withhold the next day's dose. If resolved within 24 – 48 hours of last dose, resume at the same dose. • For any blood chemistry changes requiring more than 48 hours to resolve, resume at a reduced dose. • For any events of clinical TLS, resume at a reduced dose following resolution.

ANC = absolute neutrophil count; G-CSF = granulocyte-colony stimulating factor; TLS = tumor lysis syndrome

Table 11. Toxicities Related to Pomalidomide

Toxicity	Recommended Action
Neutropenia: ANC $< 0.5 \times 10^9/L$, or febrile neutropenia (fever $\geq 38.5^\circ C$ and ANC $< 1 \times 10^9/L$)	
 • Interrupt pomalidomide treatment, follow complete blood counts weekly. Add G-CSF (at discretion of the treating physician). • ANC returns to $\geq 0.5 \times 10^9/L$ (or per local guidelines), resume pomalidomide treatment at 3 mg/day. • For each subsequent drop to $< 0.5 \times 10^9/L$, interrupt pomalidomide treatment. • ANC returns to $\geq 1 \times 10^9/L$, resume pomalidomide treatment at 1 mg less than the previous dose.^a
Thrombocytopenia: Platelet count $< 25 \times 10^9/L$	
 • Interrupt pomalidomide treatment for remainder of cycle. • Platelet count returns to $\geq 50 \times 10^9/L$, resume pomalidomide treatment at 1 dose level lower.
Angioedema: Grade 4 rash, exfoliative or bullous rash	
 • Permanently discontinue pomalidomide.
Other Grade 3/4 toxicities judged to be related to pomalidomide	
 • Interrupt pomalidomide treatment. • Restart treatment at 1 dose level lower than the previous dose when toxicity has resolved to \leq Grade 2 at the physician's discretion.

ANC = absolute neutrophil count; G-CSF = granulocyte-colony stimulating factor

a. If adverse reactions occur after dose reductions to 1 mg, then study drug should be discontinued.

Table 12. Toxicities Related to Dexamethasone

Toxicity	Recommended Action
Dyspepsia = Grades 1 – 2	Maintain dose and treat with histamine (H2) blockers or equivalent. Decrease by 1 dose level if symptoms persist.
Dyspepsia ≥ Grade 3	Interrupt dose until symptoms are controlled. Add H2 blocker or equivalent and decrease 1 dose level when dose restarted.
Edema ≥ Grade 3	Use diuretics as needed and decrease dose by 1 dose level.
Confusion or mood alteration ≥ Grade 2	Interrupt dose until symptoms resolve. When dose restarted, decrease dose by 1 dose level.
Muscle weakness ≥ Grade 2	Interrupt dose until muscle weakness ≤ Grade 1. Restart with dose decreased by 1 level.
Hyperglycemia ≥ Grade 3	Decrease dose by 1 dose level. Treat with insulin or oral hypoglycemic agents as needed.
Acute pancreatitis	Discontinue dexamethasone treatment regimen.
Other ≥ Grade 3 dexamethasone-related adverse events	Stop dexamethasone dosing until adverse event resolves to ≤ Grade 2. Resume with dose reduced by 1 dose level.

APPENDIX J. SAMPLE LIST OF PROHIBITED AND CAUTIONARY MEDICATIONS THAT MAY INTERACT WITH STUDY DRUGS

Prohibited During Part 1, Cycle 1 and Cautionary in Part 1, ≥ Cycle 2 and in Part 2, All Cycles

Strong CYP1A2 inhibitors^{††} – ciprofloxacin, enoxacin, fluvoxamine, zafirlukast
 
Strong CYP3A inhibitors[†] – boceprevir, clarithromycin, cobicistat, conivaptan, danoprevir/ritonavir, elvitegravir/ritonavir, idelalisib,* indinavir, itraconazole, ketoconazole, lopinavir/ritonavir, mibefradil, nefazodone, nelfinavir, paritaprevir/ritonavir combinations, posaconazole, ritonavir, saquinavir, telaprevir, telithromycin, tipranavir/ritonavir, troleandomycin, voriconazole
 
Moderate CYP3A inhibitors[‡] – amprenavir, aprepitant, atazanavir, cimetidine, ciprofloxacin, clotrimazole, crizotinib,* cyclosporine,* darunavir/ritonavir, diltiazem,^a erythromycin, fluconazole, fosamprenavir, imatinib,* isavuconazole, tofisopam, verapamil
 
Strong CYP3A inducers – avasimibe, carbamazepine, enzalutamine, mitotane, phenytoin, rifampin, St John's wort
 
Moderate CYP3A inducers – bosentan, efavirenz, etravirine, modafinil, nafcillin

Cautionary

Warfarin**
 
P-gp substrates – aliskiren, ambrisentan, colchicine, dabigatran etexilate, digoxin, everolimus,* fexofenadine, lapatinib,* loperamide, maraviroc, nilotinib,* ranolazine, saxagliptin, sirolimus,* sitagliptin, talinolol, tolvaptan, toptecan*
 
BCRP substrates – methotrexate,* mitoxantrone,* irinotecan,* lapatinib,* rosuvastatin, sulfasalazine, toptecan*
 
OATP1B1/1B3 substrates – atrasentan, atorvastatin, ezetimibe, fluvastatin, glyburide, rosuvastatin, pitavastatin, pravastatin, repaglinide, simvastatin acid, telmisartan, valsartan, olmesartan
 
P-gp inhibitors – amiodarone, azithromycin, captopril, carvedilol, dronedarone, felodipine, quercetin, quinidine, ronalzine, ticagrelor
 
BCRP inhibitors – gefitinib*
 
Corticosteroids – cortisone, hydrocortisone, methylprednisolone, prednisolone, prednisone, triamcinolone, betamethasone, dexamethasone

BCRP = breast cancer resistance protein; CYP = cytochrome P450; FDA = Food and Drug Administration; OATP = organic anion-transporting polypeptide; P-gp = P-glycoprotein; USPI = United States package insert

a. Moderate CYP3A inhibitor per venetoclax FDA USPI.

* These are anticancer agents; contact the AbbVie Therapeutic Area Medical Director before use.

** Closely monitor the international normalized ratio.

† If a subject requires use of these medications, use with caution and reduce the venetoclax dose by 75%. After discontinuation of the CYP3A inhibitor, wait for 3 days before venetoclax dose is increased back to the target dose.

‡ If subject requires use of these medications, use with caution and reduce the venetoclax dose by 50%. After discontinuation of CYP3A inhibitor, wait for 3 days before venetoclax dose is increased back to the target dose.

†† If a subject requires use of these medications, use with caution and reduce the pomalidomide dose by 50%.

Note: this is not an exhaustive list. For an updated list, see the following link:

<http://www.fda.gov/Drugs/DevelopmentApprovalProcess/DevelopmentResources/DrugInteractionsLabeling/ucm093664.htm>

In addition to the medications listed in this table, subjects receiving venetoclax should not consume grapefruit, grapefruit products, Seville oranges (including marmalade containing Seville oranges), or Star fruits. Herbal and natural remedies are to be avoided.

